TRIAL MANAGEMENT AND OVERSIGHT ARRANGEMENTS..... 20

 Trial Sponsorship..... 20

 Trial Management..... 20

 Individual Responsibilities..... 21

 Trial Office 22

 Data management & storage..... 22

 Confidentiality 22

 Data Monitoring Committee 23

REPORTING, PUBLICATIONS AND NOTIFICATION OF RESULTS 23

 Data Policy..... 23

 Publication 24

 Intellectual Property/Commercial Exploitation 24

PHARMACOVIGILANCE 24

 Risks to the Participants 24

 Protection against risk 26

 Potential benefits 26

 Alternatives to Participation 27

 Regulatory Approvals 27

 Study Monitoring..... 27

 Adverse Events..... 27

Oral antihypertensive regimens for management of hypertension in pregnancy

Protocol v6.0 (October2015)

Serious adverse events (SAEs).....28
REFERENCES.....30

INTRODUCTION

Preeclampsia, and in particular severe preeclampsia, represents a significant risk to maternal health. Delivery of the fetus is the definitive treatment. Treatment with magnesium sulfate clearly reduces the risk for maternal seizures, eclampsia, and probably reduces maternal mortality. Treatment of severely elevated blood pressure should reduce the risk for maternal complications such as cerebral hemorrhage, cerebral edema and posterior reversible encephalopathy syndrome (PRES). Regimens for the acute treatment of severely elevated blood pressure that have been subjected to clinical trials have generally used medications administered intravenously, (eg. hydralazine, labetalol). While these regimens are effective in lowering blood pressure, they require venous access and have the potential to reduce blood pressure rapidly, destabilizing maternal hemodynamics at the expense of the fetal condition. Careful fetal monitoring is required.

An optimal antihypertensive regime for management of preeclampsia in low-resource settings would:

- Use oral drugs that are widely available
- Reduce blood pressure in a controlled and predictable manner so as not to destabilize the fetal condition
- Be cerebro-protective maintaining a normal cerebro-perfusion pressure and pulse pressure.
- Be free of significant side effects that could limit acceptability and utilization

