Successful outcome will be considered blood pressure that reaches the target (defined as 120-150mmHg systolic and 70-100 mmHg mm Hg diastolic) within 6h without an adverse outcome. Adverse outcomes include hypotension (systolic blood pressure, <120 mm Hg and/or diastolic blood pressure <70 mm Hg and fetal compromise), caesarean section for fetal distress within or up to 2 hours after the end of the study period, severe headache and severe headache requiring discontinuation of drug, or eclampsia.

Additional maternal outcomes:

- the number of BP measures above target range
- the number of BP measures below target range
- placental abruption
- maternal side effects associated with deteriorating maternal preeclampsia or the need to change drug regimen,
 - chest pain
 - dyspnea
 - headache
 - visual symptoms (flashes, diplopia)
 - epigastric or right upper quadrant abdominal pain

- nausea or vomiting.
- maternal mortality
- maternal morbidity during or up to two hours after the study period
 - eclampsia or seizure,
 - adverse CNS outcome (stroke, cortical blindness)
 - HELLP syndrome
 - pulmonary edema (O₂ sat < 90%, abnormal chest x-ray)
 - oliguria (<25 cc/hr for 2 hours)
 - disseminated intravascular coagulation
- Caesarean delivery
- Enrollment to delivery interval

Perinatal outcomes:

- stillbirth
- neonatal death
- admission to neonatal special care unit
- neonatal morbidity
 - Apgar < 7 at 5 minutes
 - intubation at place of delivery
 - mechanical ventilation beyond resuscitation
 - respiratory distress syndrome (RDS) requiring O₂ supplementation
 - abnormal cerebral ultrasound
 - convulsions
 - bradycardia (sustained HR < 100) beyond resuscitation and requiring intervention

Measures of the use of maternal health-care resources:

- number of days in the hospital
- admission to an intensive care unit or a high dependency unit
- mechanical ventilation (any)
- dialysis

- blood transfusion

Measures of the use of neonatal health-service resources:

- days in special care baby unit
- days of oxygen use
- days of mechanical ventilation

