We hypothesize that nifedipine treatment of hypertensive parturient women will be more effective than labetalol or methyldopa in controlling high blood pressure (defined as 120-150mmHg systolic and 70-100 mm Hg diastolic) within 6h. Brown et al found that 83% of pregnant women with severe hypertension treated with nifedipine had successful lowering of blood pressure 110 to 169/80 to 109 mm Hg by 90 minutes without an adverse outcome.¹⁷ Our trial will enroll sicker patients and our goal is lower and lasting control. Based on the (scant) available literature, we hypothesize that nifedipine will control 75% of high blood

pressure within 6 hours and labetalol and methyldopa will be able to control 62.5% and 62.5%, respectively. As the subjects in the nifedipine study group will serve as a comparison group for both the labetalol and methyldopa regimens, the comparison of labetalol and nifedipine requires a sample size of 261 in each study group given a two tailed test, $\alpha=0.05$ and $1-\beta=80\%$, and a simple Bonferroni correction. Using the same statistical assumptions, with a nifedipine sample size of 261, the methyldopa study group requires 261 subjects. In order to account for loss to follow-up, we will enroll 894 women total (nifedipine: 298 women; labetalol: 298 women; methyldopa: 298 women).

Proposed Analyses

After the data are entered, they will be converted into an SPSS for Windows data file, reviewed for logical inconsistencies, cleaned, and analyzed.

For each of the regimens, we will calculate the following statistics:

- % of women who reach the target (defined as 120-150mmHg systolic and 70-100 mmHg mm Hg diastolic) within 6h without any specified adverse outcome (see above)
- % of women who reach the target (defined as 120-150mmHg systolic and 70-100 mmHg mm Hg diastolic) within 3h without any specified adverse outcome (see above)
- % of women who experience an adverse outcome. Adverse outcomes include hypotension (systolic blood pressure, <120 mm Hg and/or diastolic blood pressure <70 mm Hg and fetal compromise), caesarean section for fetal distress, severe headache or eclampsia.

- % of women who reach an intermediate target (defined as 120-159 mmHg systolic and 70-104 mmHg diastolic) within 6 hours without an adverse outcome.
- % of time systolic and diastolic blood pressure in target range

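### The adverse events that cancel a primary success leave out in-window maternal death, stroke and fetal death, so women with these events can be scored as successes

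*Protocol*

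**What the plan says.** Protocol, Study Outcomes, defines success as pressure in the target range "within 6h without an adverse outcome". It then names the events that count:

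- For low pressure, the list opens with "Adverse outcomes include hypotension (systolic blood pressure, <120 mm Hg and/or diastolic blood pressure <70 mm Hg and fetal compromise").
- For delivery, it counts a caesarean done because the fetus is in distress, if this happens in the study period or in the 2 hours that follow.
- For headache and seizure, it closes with "severe headache and severe headache requiring discontinuation of drug, or eclampsia".

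The same section places maternal mortality and "adverse CNS outcome (stroke, cortical blindness") under additional maternal outcomes, and stillbirth under perinatal outcomes. The maternal morbidity items, which include the CNS outcome, are counted during the study period or up to two hours after it. Nothing says that any of these cancels a success.

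Proposed Analyses scores success "within 6h without any specified adverse outcome (see above") and then restates the list for the percentage of women with an adverse outcome. That version has the same hypotension item and ends "caesarean section for fetal distress, severe headache or eclampsia".

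Two other sections state the primary outcome differently. Sample Size Calculation gives pressure control within 6 hours with no adverse-event clause. Data Monitoring Committee keeps the clause but times the target at 6 hours instead of within 6 hours.

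**The concern.** A success that can be cancelled by an adverse event should be cancelled by the gravest events in the same window. Here a severe headache cancels it and a stroke without seizure or severe headache does not. A caesarean for fetal distress cancels it and the death of the fetus does not.

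This sits badly with the protocol's own reasoning. The Introduction gives the purpose of treatment as "Treatment of severely elevated blood pressure should reduce the risk for maternal complications such as cerebral hemorrhage, cerebral edema" and related events, yet a cerebral haemorrhage does not by itself cancel a success. The Exclusion Criteria treat eclampsia and other CNS complications such as stroke as one class, but the list of cancelling events keeps only eclampsia.

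The gap goes beyond the primary comparison. The summary percentage of women with an adverse outcome uses the same list, so it would not count a woman who died or had a stroke without a listed event. The interim stopping rule also rests on this primary outcome.

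**Working it through.** **1. Is the list closed?** Study Outcomes introduces it with a word that could be read as open-ended. Proposed Analyses and Data Monitoring Committee, however, both tie success to specified adverse outcomes, and Proposed Analyses repeats the same four types. The text gives an analyst no ground for adding stroke or death.

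**2. Scoring of hypothetical records.** Each woman first reaches target at 1 to 2 hours and has no other listed event. The study period is taken as the first 6 hours.

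| Event after target is reached | Study Outcomes / Proposed Analyses (within 6h, list) | Data Monitoring Committee (at 6h, list) | Sample Size Calculation (pressure only) |
|---|---|---|---|
| Stroke at 4h, no seizure or severe headache | Success | Success if in target at 6h | Success |
| Fetal death at 5h, vaginal delivery | Success | Success if in target at 6h | Success |
| Maternal death at 5h | Success | Failure (no 6h pressure in target) | Success |
| Fetal distress at 5h, caesarean, live baby | Failure | Failure | Success |
| Severe headache at 6h | Failure | Failure | Success |

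The first two columns show the inversion, and the three columns differ from one another.

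**3. The plan's own sample size.** Inputs from Sample Size Calculation: p1 = 0.75, p2 = 0.625, 80% power, two-sided 0.05 with Bonferroni for two comparisons, so α = 0.05/2 = 0.025. With p̄ = 0.6875:

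n = [z(1−α/2)·√(2p̄(1−p̄)) + z(1−β)·√(p1(1−p1) + p2(1−p2))]² / (p1−p2)²

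= [2.2414 × √0.4297 + 0.8416 × √0.4219]² / 0.125² = 260.1, rounded up to 261.

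This matches the stated 261 per arm. Power with 261 is 80.2%.

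**4. Effect of recoding.** Assume that a share q of would-be successes, equal in the arms, becomes failures, and that the planned 75% and 62.5% apply to the composite success. The rates become 0.75(1−q) and 0.625(1−q). The women recoded number 298 × 0.75 × q with nifedipine and 298 × 0.625 × q in each other arm.

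| q (assumed) | Success rates | Difference (points) | Women recoded per 298 | Power, 261 per arm | n per arm for 80% |
|---|---|---|---|---|---|
| 0.5% | 74.6% v 62.2% | 12.44 | 1.1 / 0.9 | 79.5% | 265 |
| 1% | 74.25% v 61.9% | 12.38 | 2.2 / 1.9 | 78.7% | 269 |
| 2% | 73.5% v 61.25% | 12.25 | 4.5 / 3.7 | 77.3% | 278 |

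The enrolled 298 per arm exceeds the required n in every row, although that margin is meant for loss to follow-up.

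**The case against.** The strongest reply is that this is a design choice. Objectives makes efficacy the primary aim and puts adverse, maternal and fetal outcomes under the secondary aims. Every omitted event is a named outcome, adverse events are reviewed at the interim analysis, an arm can be dropped for safety, and serious events are reported. No harm is lost to the trial. That is true and limits the importance of the point. It does not explain why severe headache belongs in the efficacy endpoint and stroke does not: once the sponsor chose a success with a safety condition, the condition should not leave out the worst in-window events.

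A second reply is that the cases are rare and narrow. Many such women would fail anyway through a listed event, such as severe headache or eclampsia with a stroke, or hypotension with fetal compromise. On the at-6h wording, a death before 6 hours is already a failure. This also stands, and it is why the effect on the numbers is small.

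A reader might infer more than the documents support:

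- **That a death or stillbirth days later is wrongly scored.** A 6-hour endpoint has no reason to absorb late events. The point covers only the study period and the 2 hours after it.
- **That the list favours one drug.** The protocol links headache with nifedipine, but counting it works against the protocol's own hypothesis. No event rates by arm are given, so no direction of bias can be shown.
- **That placental abruption must also be listed.** The protocol states no window for it, and its harmful cases are largely caught by fetal death or caesarean for fetal distress.
- **That stopping the drug for any significant side effect should cancel success.** This would bring an undefined judgement by an unblinded clinician into the primary outcome.

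**Conclusion.** The point holds under the within-6h wording of Study Outcomes and Proposed Analyses. A woman who reaches target and then has an in-window maternal death, adverse CNS outcome or fetal death, with no listed event, is scored a success, and is also missed by the adverse-outcome percentage. On the at-6h wording the gap is narrower but remains for stroke and fetal death when the 6-hour pressure is in target.

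This is a fault in what success means. The sample size arithmetic is intact: 261 reproduces exactly. On assumed recoding of 0.5-2% of would-be successes, equal across arms, about 1 to 4.5 women per arm of 298 change status and power with 261 per arm falls by 0.7 to 2.9 points (80.2% to 79.5-77.3%). Those rates are assumptions. A reader might infer a material distortion of the planned 12.5-point difference, but that would need the events to fall almost entirely in one arm, and nothing in the protocol supports this.

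**What to change.** In Study Outcomes and in Proposed Analyses, add three items to the listed adverse outcomes, each limited to the study period or up to 2 hours after it: maternal death; adverse CNS outcome (stroke or cortical blindness); and death of a fetus alive at 0h. Keep all three as separate outcomes as well. Make Sample Size Calculation and Data Monitoring Committee use the same primary outcome definition, including one choice between within 6h and at 6h. Settle this before any comparison by arm, so that the gravest cases in an open-label trial are not adjudicated one by one.

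The cost is small: a sentence in two places and aligned wording in two others. Maternal and neonatal outcomes are already collected on Forms 4 and 5, and the CNS outcome already has the 2-hour extension. Timing needs one addition. Fetal heart rate is scheduled only at 0 and 6 hours and Form 5 may be abstracted from charts, so the time of any fetal death (or of its diagnosis) should be recorded. The other downside is a slightly lower success rate.

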A post-study interview with the woman will be conducted once she is stable and prior to her discharge from the study hospital. Women will be interviewed and asked about their experience with pain and side effects. Women will be asked to rate their overall experience on a categorical five-point scale from 'very unsatisfied' to 'very satisfied'. Instruments will be informed by prior research on the acceptability of new medical technologies for delivery of magnesium sulphate among Indian women.

Data will be collected throughout the woman's admission, with data collection stopping postnatally at time of discharge or maternal death. No further follow-up is planned.

Pilot Study

Given the uncertainty of the effect of each of these drugs on this population, we will conduct a pilot study (n=30) prior to the start of the trial. The purpose of this pilot is to test the feasibility of the study protocol as designed. Women will be allocated serially to one of three oral antihypertensive regimens regimens: methyldopa (n=10), labetalol (n=10), or nifedipine (n=10).

The primary aim of the pilot study is to assess the three proposed drug regimens and, potentially, reveal the need for a lower dose. Methyldopa may not be effective for acute control of severe hypertension. However, in many settings where labetalol or nifedipine are not available, methyldopa is the oral drug of choice. Given our concerns about the slow onset and general lack of potency of

methyldopa, we are conducting a pilot study to assess whether it is appropriate to include it in the trial. If the success rate in any of the three arms is less than 30% (3/10) then the investigators will assess whether to include the regimen in the RCT. The secondary aims of the pilot are to (1) assess adverse outcomes and necessity for additional antihypertensive treatment among women in the three study arms; and (2) to evaluate data collection tools (including use of the Glasgow Coma Scale and assessments of women's attitudes post-treatment) in the subsequent trial.

Required ethical approvals for the pilot study have been obtained from Government Medical College Nagpur and the University of British Columbia.

Study Assessment and Data Collection Forms

Form 1: Screening Form. This form will determine a woman's eligibility for enrollment in the study. The form will also document basic demographic characteristics and obstetrical history.

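### Data collection is tied to the woman's discharge or death, so listed in-hospital neonatal outcomes have no end point of their own and, read literally, are cut short

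*Protocol*

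**What the plan says.** The last paragraph of Study Outcomes (just before Pilot Study) sets one stopping rule for the trial. Data are gathered over the woman's admission, "with data collection stopping postnatally at time of discharge or maternal death. No further follow-up is planned".

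The outcome lists in the same section include "neonatal death" among the perinatal outcomes and, under neonatal health-service resources, "days in special care baby unit", "days of oxygen use" and "days of mechanical ventilation". None has a time window. Maternal stay is listed separately, as "number of days in the hospital".

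Three other places bear on the point:

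- **Study Assessment and Data Collection Forms, Form 5 (Neonatal Outcomes).** The clinician records how the baby finally fared. Abstraction from charts is permitted where charts can be had. No end date is given, and no exception to the stopping rule is made.
- **Pharmacovigilance, Protection against risk.** After study treatment is stopped, data collection runs to discharge from the study hospital. Nothing is said about the baby.
- **Inclusion Criteria and Objectives.** Women enter from 28 weeks' gestation, and comparing maternal and fetal outcomes across the arms is a secondary aim.

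**The concern.** A baby can stay in special care after its mother has gone home. With entry from 28 weeks, preterm births followed by such stays are foreseeable. If the trial record closes with the mother's discharge, the three day counts stop there and a later in-hospital death is missed. If the mother dies, collection stops while the baby may still be alive and in care.

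Two consequences would follow. The neonatal outcomes would be under-counted in every arm. Differences between arms in days of care would also shrink, because long stays are cut at a limit unrelated to the baby's course. A statistical analysis plan could define an analysis window, but it could not restore data that the protocol says will not be collected. The point therefore belongs in the protocol.

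**Working it through.** **Step 1: whose discharge?** The stopping sentence does not name the person discharged. Its subject is the woman's admission and its alternative event is maternal death, so her discharge is the natural reading. No section sets a separate stopping point for the baby.

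**Step 2: set the sections side by side.**

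| Section | What it implies for the baby |
|---|---|
| Study Outcomes, stopping rule | Collection ends with the mother's discharge or death |
| Study Outcomes, lists | Death and days of care wanted, no window |
| Form 5 | Final outcome wanted, no end point, charts optional |
| Protection against risk | Ends at discharge from the study hospital, baby not mentioned |

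The stopping rule and Form 5 pull in different directions. Staff following the first would close the baby's record with the mother's. Staff following the second could keep it open. The two hospitals could differ in practice.

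**Step 3: what is affected.** Items settled at or near birth (stillbirth, Apgar at 5 minutes, intubation at the place of delivery) are not touched. Neonatal death and the three day counts are. Everything up to the mother's discharge or death is still recorded; only what comes later is at risk.

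**Step 4: size.** The protocol gives no length of stay for mother or baby and no neonatal event rate, so there is no plan figure to reproduce on this point. For illustration, assume an exponential special-care stay with mean *m* days and a maternal discharge *c* days after birth, with both clocks starting at birth. Then:

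- recorded mean = m × (1 − exp(−c/m))
- share of days lost = exp(−c/m)

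| m (days) | c = 3 | c = 5 | c = 7 |
|---|---|---|---|
| 5 | exp(−0.6) = 55% | exp(−1) = 37% | exp(−1.4) = 25% |
| 10 | exp(−0.3) = 74% | exp(−0.5) = 61% | exp(−0.7) = 50% |

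Across these assumptions, 25% to 74% of days are lost.

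**Step 5: attenuation.** Suppose the true means were 10 and 8 days in two arms, both cut at day 5:

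- 10 × (1 − exp(−0.5)) = 3.93 days
- 8 × (1 − exp(−0.625)) = 3.72 days

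A true difference of 2 days would be recorded as about 0.2 day. The 2-day difference is hypothetical, since nothing in the protocol predicts one. The cut-off is the same in both arms, so this example shows shrinkage only and says nothing about unequal windows.

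**Step 6: the primary outcome.** The protocol's 261 women per arm reproduces for 75% against 62.5% with 80% power and a two-sided level of 0.05/2 = 0.025, without continuity correction. It concerns blood pressure control within 6 hours and does not depend on the neonatal window.

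**The case against.** The best counter-argument is Form 5. It is separate from the maternal form, it asks for the baby's final outcome, it allows chart abstraction, and nothing in it closes the record at the mother's discharge. The investigators may well have meant to follow babies for their whole hospital stay. This stands as far as it goes: a reader might infer that truncation is certain, and the protocol does not establish that. It does establish an unresolved conflict. Form 5 states no end point and no exception to the stopping rule, and Form 4 uses parallel wording for the woman.

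Three other strong readings are tempting and not supported:

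- **That neonatal data are lost whenever the mother dies.** Only events after her death could be missed. The protocol gives no expected number of maternal deaths, and nothing in it shows how the baby's risk changes at that time.
- **That the window differs by arm and biases the comparison.** Maternal stay is an outcome measured after randomisation in an open-label trial, so this could happen. But no section says that stay is expected to differ by arm. If stays are similar, the effect is attenuation and not bias in favour of one arm.
- **That a quarter to three quarters of special-care days will be lost here.** That range is a property of the assumed distribution, means and cut-offs.

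It is also fair to say that following participants only in hospital is an openly declared choice in a pragmatic trial, and that the neonatal items are not among the statistics named individually under Proposed Analyses. Both points limit the importance of the finding. Neither explains why the baby's in-hospital record should end with the mother's.

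**Conclusion.** The point holds as an inconsistency in the data-collection rule. The protocol lists neonatal outcomes that can run past the mother's discharge or death, ends collection at that time, and leaves Form 5 without an end point. Followed literally, the rule under-counts in-hospital neonatal deaths and days of special care, oxygen and ventilation, and it attenuates arm differences in the day counts.

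The direction follows from the text, given the natural reading that the discharge is the woman's and given that some babies stay longer than their mothers. The size is unknown, and the illustrative figures rest wholly on assumed stays. Unequal windows by arm remain a possibility only. The damage is confined to secondary outcomes; the primary outcome and the sample size stand. The change is worth making because it is cheap and because no later analysis can recover data that were never collected.

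**What to change.** Amend the stopping rule in Study Outcomes along these lines:

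> *Maternal data are collected until the woman's discharge or death. Neonatal data (Form 5) are collected by chart abstraction until the baby's own discharge from the study hospital or the baby's death, whichever comes first, including after the mother's discharge or death.*

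Then align the other sections:

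- In the outcome lists, define neonatal death as death before the baby's discharge from the study hospital, and state that the three day counts cover the same stay.
- In the description of Form 5, give the same end point.
- In Protection against risk, say that the end of collection differs for mother and baby.

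I would not use a fixed neonatal age instead. It would either require contact after discharge, which the protocol excludes, or have to be set so early that the truncation remained.

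The limits should be plain. Deaths after the baby goes home, and events after transfer to another hospital, would still not be captured. The outcomes should therefore be labelled as in-hospital outcomes.

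The cost is a short amendment and some additional chart abstraction for babies still in the unit. The four research coordinators named under Individual Responsibilities already collect data at the two sites. No new visits or procedures are needed.
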